#### Primary Endpoint

1. Uterine tone score as recorded at 10 minutes following the administration of the second-line uterotonic.

#### Secondary Endpoints

1. Need for an additional uterotonic agent after the study drug,
2. Uterine tone score as recorded at 5 minutes following the administration of the second-line uterotonic,
3. Number of units of blood products transfused from  $t_0$  to  $t_{final}$  ( $t_0$  = time of delivery;  $t_{final}$  = 24 hours after delivery)
4. Need for a surgical or radiologic intervention to control bleeding.
5. Quantitative intrapartum blood loss
6. Pre- vs post-delivery hemoglobin values.
7. Maternal morbidity: admission to the intensive care unit postpartum, postoperative infection, transfusion reaction, acute kidney injury, hypovolemic shock, or vasopressor requirement, study medication side effects.

#### Subject Costs

There will be no extra costs to the subjects related to the conduct of this study, as there are no additional medications or tests to be used that are not already the routine standard of care. Methylergonovine and carboprost used in the study will be stocked as needed by the inpatient hospital pharmacy in the usual manner. Subjects and/or their insurance companies will be responsible for all their medical and surgical procedures and care as associated with their delivery.

## VI. BIOSTATISTICAL ANALYSIS

- a. Specific data variables being collected for the study (e.g., data collection sheets).

Baseline patient characteristics will be collected and documented on data collection sheets. These characteristics will include:

1. patient MRN
2. randomization group
3. age
4. height, weight, BMI
5. gravidity and parity
6. baseline hematocrit and platelet count measured at the time of admission or on the day of delivery

- b. Statistical methods

The balance of patient characteristics between the two groups before intervention will be evaluated using standardized differences. Shapiro-Wilk test will be used to confirm whether the primary endpoint, uterine tone score 10 minutes after drug administration, satisfies the normality assumption. Multiple linear regression will be conducted when normality assumption satisfied. In the case when the normality assumption is not established, log transformation/box-cox transformation of the outcome will be carried out before modeling. For secondary endpoints that are dichotomous, logistic regression will be used to

examine the intervention effect after adjusting for potential confounders. For continuous secondary endpoints, such as intrapartum blood loss, we will evaluate its distribution before performing appropriate modeling. Trial site will be included as a covariate in all models to adjust for the stratification of randomization by hospital.

c. Power analysis (e.g., sample size, evaluable subjects, etc.)

Assuming a common within-group standard deviation in uterine tone score of 1.9 points, a minimum sample size of 41 randomized patients per group would provide 80% power at a two-sided alpha level of 0.05 to detect a 1.2 point difference in mean uterine tone score at 10 minutes post secondary uterotonic administration between groups using a two-sample t-test. A total of 50 patients per group (100 patients total) will need to be randomized to account for protocol violations. Since we currently perform 175 C/S monthly at BWH, and approximately 20 patients undergoing non-emergent C/S receive methergine or hemabate for uterine atony each month, we anticipate needing to enroll 1250 patients in total to be able to randomize 100 patients to receive the study intervention.

The within-group standard deviation estimate of 1.9 is based on the observed standard deviation in uterine tone score (averaged between raters) at 10 minutes post-delivery amongst patients in our previous study (The Inter-rater Reliability of a 0 to 10 Uterine Tone Score) who received a secondary uterotonic. The minimal clinically important difference of 1.2 points is based on the upper limit of the 90% confidence interval for the difference in uterine tone score (averaged between raters) at 3 minutes post-delivery between patients who did and did not receive a secondary uterotonic (difference in means [90% CI]: -2.3 [-3.5, -1.2]).

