## II. **SPECIFIC AIMS** (Research Objectives)

We hypothesize that the administration of methergonovine will be associated with a 1 point greater reduction in uterine tone (on a 0-10 scale) at 10 minutes after administration compared to carboprost.

1. The primary outcome will be the uterine tone score on a 0 to 10 scale 10 minutes after administering the study drug. A score of 0 will mean the uterus has 'no tone'. A score of 10 will mean there is 'excellent tone'.
2. Secondary outcomes will include:
  - a) change in uterine tone from the time of study drug administration to 5 minutes later,
  - b) administration of an additional uterotonic agent after the first study drug
  - c) number of transfused blood products within 24 hours from the time of delivery,
  - d) any surgical intervention intended to control bleeding: i.e. Bakri balloon, O'Leary stitch, d&e, exploratory laparotomy, B-Lynch sutures, hysterectomy or interventional radiology artery embolization,
  - e) intraoperative quantitatively measured blood loss (QBL),
  - f) pre-delivery to postpartum change in serum hemoglobin,
  - g) vasopressor requirement or hypovolemic shock
  - h) postpartum admission to the intensive care unit (ICU),
  - i) need for postoperative mechanical ventilation,
  - j) nausea, vomiting, or diarrhea, abdominal pain, shortness of breath, headache, blurred vision, anxiety, chest pain, sweating, or palpitations within 2 hours postpartum
  - k) hypertensive emergency (SBP>/=160 or DBP>/=110)
  - l) EKG changes indicative of myocardial ischemia,
  - m) acute renal dysfunction,
  - n) length of postoperative hospital stay,
  - o) postpartum acute lung injury or circulatory fluid overload in the context of blood product transfusion,
  - p) allergic reaction deemed the result of blood product transfusion

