The obstetrician and nurse, involved in the cases as well as the study investigator will be blinded to the study group assignments. All physician co-investigators (with the exception of the principal investigator) and the statistician will be blinded to study group assignments throughout the study. As such, these co-investigators will not be involved in the obstetric care of the study subjects, with the following one exception: Every effort will be made to keep the study investigator who consented the subject out of the operating room and uninformed in the subject's clinical care in all cases. However occasionally, due to staffing challenges and clinical acuity of a patient's case (e.g. massive hemorrhage), the anesthesiology attending or fellow who consented the patient may need to be involved in the patient's intraoperative or postoperative care. To minimize any chance of patient coercion and bias in clinical decision-making, the consent process will occur first with the study investigator anesthesiologist. Only after consent is complete and the patient enrolled will the same anesthesiologist who consented the patient end up caring for the patient. This scenario will only occur in situations when a staffing shortage occurs or the case requires additional help due to a life-threatening situation. Everything possible will be done to avoid that situation. Thus the patient will agree to participate in the study in advance of forming any physician-patient relationship with the study investigator, and the study investigator will only affect clinical care as a helper in case of clinical necessity, not as the leader of clinical decision-making (i.e. the study investigator will not be the primary anesthesiologist of record for the case).

The study drug will consist of either:

1. 0.2mg methylergonovine, or
2. 0.25mg 15-methyl prostaglandin F2a

The anesthesiologist will administer the study medication in a 1mL syringe intramuscularly in the patient's deltoid muscle. Each patient will have both medications available in the fridge where hemorrhage medications are stored, so that the second of the 2 drugs can be easily administered in succession if an additional agent is needed.

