Second-Line Uterotonics in Postpartum Hemorrhage: A Randomized Clinical Trial

NCT: 03584854

April 04, 2018

*Biostatistical Analysis Plan*

An a priori power analysis determined that enrollment of 37 patients per group would provide 80% power at a 2-sided alpha level of 0.05 to detect a 1-point difference, with estimated within-group standard deviation of 1.5, in mean uterine tone at 10 minutes after study drug administration using a two-sample t-test. Randomization of 100 patients was planned to account for protocol violations. Uterine tone at 10 minutes (primary outcome) and 5 minutes (secondary outcome) after study drug administration were compared between groups with adjustment for baseline tone and trial site using the generalized estimating equations (GEE) method with an identity link to account for the correlation between repeated measurements on the same patient. The primary analysis was a complete-case analysis, where 3 patients (3%) missing uterine tone at baseline and/or 10 minutes were excluded from the analysis. A multiple imputation sensitivity analysis was also performed which used the multivariate imputation by chained equations approach to impute missing uterine tone values using observed tone measurements (baseline, 5, and 10 minutes), parturient characteristics (age, race, BMI, parity), infant characteristics (number of fetuses, infant birth weight), trial site, interventions (randomized study drug, administration of second study drug, intraoperative transfusion), and outcomes (intraoperative blood loss, change in hematocrit from baseline to 24 hours post-delivery) to create 10 complete datasets. The primary outcome was compared in each of the 10 imputed datasets, and results combined using Rubin's rule.

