All continuous secondary outcomes were initially assessed for the normality of residuals from a multivariable linear regression model with trial site and baseline uterine tone as covariates. Outcomes displaying normally distributed model residuals were analyzed using multivariable linear regression, with effect size presented as adjusted difference in means with 95% CI. Outcomes with all non-zero values that displayed skewed linear regression model residuals were natural log-transformed and analyzed using multivariable linear regression, with effect size presented as adjusted ratio of geometric means with 95% CI. Outcomes containing at least one zero value that presented skewed linear regression model residuals were compared between groups using multivariable quantile regression, with effect size presented as adjusted difference in medians with 95% CI.

All binary outcomes were initially considered for comparison using multivariable logistic regression (for single measurements) or generalized estimating equations with a logit link (for repeated measurements) with trial site and baseline uterine tone as covariates. If the multivariable regression converged, effect size was presented as adjusted odds ratios with 95% CI. If the model did not converge due to low incidence, groups were compared using a Fisher's exact test and effect size presented as risk difference with exact 95% CI.

Time to receive second study drug was compared between groups using a multivariable Cox proportional hazards model, with effect size presented as adjusted hazard ratio with exact 95% CI. Complete-case analysis was performed for all secondary outcomes. All analyses were performed using SAS software version 9.4 (SAS Institute, Cary, NC).

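### The protocol and the SAP give different primary analyses with no statement of which governs, and the protocol's transform rule fails if any score is 0

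*Protocol*

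**What the plan says.** **Protocol, section VI.b (version dated 04/19/2022).** The outcome itself is tested first: "Shapiro-Wilk test will be used to confirm whether the primary endpoint, uterine tone score 10 minutes after drug administration, satisfies the normality assumption." No significance level is attached to the test. If it passes, multiple linear regression follows. If it does not: "In the case when the normality assumption is not established, log transformation/box-cox transformation of the outcome will be carried out before modeling." On covariates the section says: "Trial site will be included as a covariate in all models to adjust for the stratification of randomization by hospital." It does not mention baseline tone.

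**SAP (dated April 04, 2018).** The 10- and 5-minute scores are "compared between groups with adjustment for baseline tone and trial site using the generalized estimating equations (GEE) method with an identity link," with no normality check and no transform. On the analysis set it says: "The primary analysis was a complete-case analysis, where 3 patients (3%) missing uterine tone at baseline and/or 10 minutes were excluded from the analysis." Multiple imputation is a sensitivity analysis. A residual check and a rule for zeros do exist, but only in the paragraph on continuous secondary outcomes: "Outcomes with all non-zero values that displayed skewed linear regression model residuals were natural log-transformed," while skewed outcomes that contain a zero go to quantile regression.

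**Scale and blinding.** Protocol section II states the hypothesis in points ("1 point greater reduction in uterine tone (on a 0-10 scale) at 10 minutes after administration compared to carboprost") and makes 0 the lowest valid score. Section V says that "the statistician will be blinded to study group assignments throughout the study."

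**The concern.** A trial needs one primary analysis, fixed before the allocation is known. Here there are two. They differ in covariates, in how repeated scores are handled and, when the normality test fails, in the scale of the effect. Neither text refers to the other or claims precedence.

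The dates do not help. The SAP carries the earlier date, yet it is written in the past tense and gives the number of patients with missing tone. Not all of that text can come from the planning stage, so its date does not show when the GEE was chosen.

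The protocol's rule also leaves open choices of its own: the test level, which of two transforms to use, and what to do with a 0. The transform branch can give an effect that is not in points, although the hypothesis and both sample-size calculations are in points.

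**Working it through.** **1. The plan's own figures.** For two means, n per group = 2(1.95996 + 0.84162)² × SD²/d² = 2 × 7.849 × SD²/d².

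- Protocol VI.c, d = 1.2, SD = 1.9: 2 × 7.849 × 3.61/1.44 = 39.4, so 40. The exact t calculation gives 40.34, so 41, as stated (power 0.807).
- SAP, d = 1, SD = 1.5: 2 × 7.849 × 2.25 = 35.3, so 36. The exact t calculation gives 36.31, so 37, as stated (power 0.808).

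Both reproduce, and both are for untransformed points.

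**2. Side by side.**

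| | Protocol VI.b | SAP |
|---|---|---|
| Check on the 10-minute score | Shapiro-Wilk on the score, level not given | none |
| Model | linear regression, after log or Box-Cox if the check fails | identity-link GEE, 5- and 10-minute scores |
| Covariates named | site | baseline tone, site |
| Effect scale | points, a ratio (log), or a power scale (Box-Cox) | points |
| Rule for a score of 0 | none | not needed |

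**3. A score of 0.** log(0) is minus infinity. Estimating the Box-Cox λ by maximum likelihood uses the term (λ − 1)Σ log y, which is not finite if any y is 0; scipy's routine rejects such data. An offset would make the log computable, but its value matters. With means 5 and 3.8, SD 1.9, 50 per arm and whole points cut to 0–10, t-test power is 0.88 on raw scores, 0.85 with log(y + 1), 0.83 with log(y + 0.5) and 0.67 with log(y + 0.01).

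**4. How often the branch is reached.** From protocol VI.c: SD 1.9, difference 1.2, 50 per group. Assumed, because the documents do not give them: normal scores, the recording increment, clipping to 0–10, all 50 per arm analysed, overall mean 5 to 8, test level 0.05. There were 4000 trials per cell; Monte Carlo standard error is about 1 percentage point or less.

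| % of trials | mean 5 | 6 | 7 | 8 |
|---|---|---|---|---|
| Test fails, whole points | 92 | 99.8 | 100 | 100 |
| Test fails on within-group residuals, whole points | 40 | 50 | 77 | 99.7 |
| Test fails, half-points | 10 | 19 | 90 | 100 |
| Test fails, tenths | 3 | 6 | 67 | 100 |
| Test fails and a 0 is present, whole points | 62 | 25 | 5 | 0.7 |
| Test fails and a 0 is present, half-points | 4 | 3 | 4 | 0.3 |

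**5. Effect of the transform where it can be computed.** Among whole-point trials that fail the test and contain no 0, raw and log analyses disagree on p<0.05 in 3–7%, and raw and Box-Cox in 0.3–2%. The 95% interval for λ includes 1 in about 94%, 99%, 95% and 41% of these trials at means 5, 6, 7 and 8.

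**6. Difference between the documents.** Further assumptions: whole points; baseline mean 3, SD 1.9; correlation 0.7 between the 5- and 10-minute scores; 5-minute mean 0.5 lower with the same 1.2-point difference; second site (1250 − 950)/1250 = 24% of patients, from the enrollment figures in the IRB application, with no site effect. The GEE uses an independence working correlation, an uncorrected sandwich standard error and a treatment-by-time term. VI.b is read as regression on arm and site only.

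| Correlation of baseline with follow-up | 0 | 0.3 | 0.5 |
|---|---|---|---|
| VI.b untransformed and GEE disagree on p<0.05 | 2% | 6% | 9% |
| VI.b Box-Cox and GEE disagree | 2–3% | 5–7% | 9–11% |
| VI.b log and GEE disagree | 4–7% | 8–10% | 11–14% |
| GEE standard error ÷ VI.b standard error | 0.99 | 0.94–0.95 | 0.86–0.87 |

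The last row is close to √(1 − ρ²) = 1, 0.954 and 0.866, the gain expected from adjusting for baseline. At correlation 0.5, power is 86–88% for VI.b and 93–95% for the GEE.

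**The case against.** The SAP is the dedicated analysis document, names a single model and reports it as carried out. The natural reading is that the GEE is primary and VI.b is a summary that was never updated. On that reading the normality test and the zero problem do not arise. This is right as far as it goes: the transform defect is conditional on VI.b governing. But no text says that the SAP governs, and a SAP that already contains missing-data counts cannot show by its date that its model came first.

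The sizes can also be challenged, and much of this stands.

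- Silence on baseline tone is not exclusion. If VI.b's regression includes it, disagreement with the GEE falls to 1.1–1.7% at every correlation. Nearly all of the 6–9% therefore comes from that covariate.
- Part of the remainder comes from the uncorrected sandwich standard error, which the SAP does not specify. It runs at about 0.98 of the model-based one, and null rejection is about 5.7–6.5% against 4.9–5.6% for baseline-adjusted regression.
- The failure rates depend on a mean and a recording increment that the documents do not give.
- Where the transform can be computed, it seldom changes significance, and the blinding of the statistician limits outcome-driven choice.

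Finally, adopting the SAP's model means adopting the more powerful of the two while its prespecification is unproven. That is why the date must be disclosed and the other regression shown.

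**Conclusion.** The concern holds, on the text alone. The two documents describe different primary analyses, nothing sets precedence, and the protocol's fallback leaves the transform unchosen and cannot be run with a permitted score of 0. The SAP's rule for zeros covers secondary outcomes only and does not fill the gap.

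The numerical effect is modest. If VI.b adjusts for site only, its untransformed regression and the GEE give different significance calls in about 2% to 9% of simulated trials across baseline correlations of 0 to 0.5. If VI.b also adjusts for baseline tone, the figure is 1% to 2%. With whole-point scoring and VI.b in force, the transform branch would be the usual path; with finer scoring and a mean near 5 or 6 it would be uncommon. These rates illustrate the problem under stated assumptions and do not measure this trial. The main damage is to the reader's ability to tell which primary result was planned. It should be fixed.

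**What to change.** - In protocol VI.b, remove the Shapiro-Wilk test and the transformation for the primary endpoint.
- In both documents, name one model: the SAP's GEE on the untransformed score, adjusted for baseline tone and site, with the adjusted mean difference in points and its 95% CI. If the 5- and 10-minute scores share one GEE, specify the 10-minute contrast.
- State which document governs.
- Record the date on which this model was fixed and whether that was before unblinding.
- Report VI.b's untransformed, site-adjusted regression alongside, so that readers can see whether the choice mattered.
- Present any transformed analysis only as a sensitivity analysis, with one named transform and a stated offset.

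No new data are needed: the intraoperative tone sheet already holds the 0-, 5- and 10-minute scores, and site is known. The cost is disclosure. Because the SAP text already reports missing-data counts, the change has to be dated and acknowledged as such.

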At the time of administration of the first study drug, the anesthesiologist will ask the obstetrician to rate the uterine tone on a scale of 0 to 10 (0 being 'no tone', 10 being 'excellent tone'). The anesthesiologist will then set a timer. After administration of the study drug, patient care will receive our usual standard of care. At 5 and 10 minutes from the onset of timing, the anesthesiologist will once again ask the obstetrician for a rating of uterine tone between 0 and 10. These values will be recorded by the anesthesiologist on a Uterine Tone Score Intraop Data Collection sheet included in the sealed envelope provided by the investigator.

If an additional uterotonic agent is requested by the obstetrician, the unblinded anesthesiologist will prepare the other drug, again in a-1mL syringe. Timing of this administration will be noted on the study record sheet. All other medications and interventions will proceed as usual and in an unblinded fashion.; If uterine tone remains unsatisfactory, identity of the study drugs will remain blinded, if possible. Any repeat administrations of carboprost or methylergonovine will be given by the anesthesiologist based on the timing of administration of the 2nd study drug.

The obstetric physicians and nurses caring for the patient will document quantitatively measured blood loss during the delivery. The volume of blood mixed with amniotic fluid in the graduated suction jars and the number of sponges soaked with blood will be noted. In addition to baseline serum hematocrit, postpartum serum hematocrit and platelet count, will be evaluated on the first postoperative day after C/S. The change in serum hematocrit will be compared among study groups.

At the end of the C/S, the anesthesiologist will complete the Randomization Sheet, documenting the patient MRN and study ID number. They will return the Randomization sheet and the Uterine Tone Score Intraop Data Collection sheet in the [previously sealed] envelope to a locked room on L&D where all paper documents for the study will be temporarily stored until the unblinded principal investigator collects the sheets (on the same day as subject enrollment) and brings them to a locked filing cabinet in a locked office to which only the principal investigator has access.

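### The planning SD of 1.9 is for rater-averaged scores, but the endpoint is one obstetrician's rating; other things equal it is too small, and the stated 80% power at 41 per group has almost no slack

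*Protocol*

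**What the plan says.** Section VI.c of the protocol sets the calculation out in full. The SD enters as "Assuming a common within-group standard deviation in uterine tone score of 1.9 points". The target is "to detect a 1.2 point difference in mean uterine tone score at 10 minutes post secondary uterotonic administration between groups using a two-sample t-test", and the result is that "a minimum sample size of 41 randomized patients per group would provide 80% power at a two-sided alpha level of 0.05". The number is then raised: "A total of 50 patients per group (100 patients total) will need to be randomized to account for protocol violations".

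The next paragraph gives the source of the SD: the "observed standard deviation in uterine tone score (averaged between raters) at 10 minutes post-delivery amongst patients in our previous study", restricted to those "who received a secondary uterotonic".

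The endpoint is measured differently. Section V has a single rater: at 5 and 10 minutes "the anesthesiologist will once again ask the obstetrician for a rating of uterine tone between 0 and 10". The Primary Endpoint section fixes the clock: "Uterine tone score as recorded at 10 minutes following the administration of the second-line uterotonic". No text in either document converts the rater-averaged SD into a single-rater SD.

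The SAP states another basis: SD 1.5, a difference of 1 point and 37 per group, also for a two-sample t-test. Its primary comparison adjusts for baseline tone and trial site. The protocol's statistical methods name trial site as a covariate but not baseline tone.

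**The concern.** The SD used for planning belongs to a less noisy measurement than the one the trial will analyse. A score averaged over raters carries only a fraction of the rater error, and a single rating carries all of it. Unless raters agree perfectly, the single-rating SD is the larger of the two, other things equal.

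What is at stake is the stated power at the minimum size, and what the extra 9 patients per group (50 − 41) are for. The protocol assigns those 9 to protocol violations. If part of them is needed only to bring power back to 80%, less is left for that purpose.

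**Working it through.** **Inputs from the protocol (VI.c):** difference 1.2, SD 1.9, two-sided alpha 0.05, 41 per group as the minimum, 50 per group randomized, two-sample t-test.

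**Inputs not in the documents, so assumed:** the number of raters averaged, k, and the single-rater reliability, ICC (the share of single-rating variance that lies between patients). Rater errors are taken as independent with equal variance. The difference is held at 1.2.

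**Step 1: reproduce the plan's figure.** The standardized difference is 1.2/1.9 = 0.632. The noncentral t gives 40.3 per group for 80% power, rounded up to 41. Power at 41 per group is 80.7%. The stated figure is correct for its inputs.

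**Step 2: find the slack.** Solving for the SD at which power is exactly 80%:
- at 41 per group, SD 1.916
- at 50 per group, SD 2.12

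**Step 3: convert the SD.** The variance of a mean of k ratings is the single-rating variance times ICC + (1 − ICC)/k. Hence

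SD(single) = 1.9 / √(ICC + (1 − ICC)/k).

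For k = 2 and ICC 0.6: 1.9/√0.80 = 2.12. For k = 2 and ICC 0.9: 1.9/√0.95 = 1.95.

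Setting SD(single) to 1.916 with k = 2 gives ICC = 2 × (1.9/1.916)² − 1, or about 0.97. Below that, unadjusted power at 41 per group is under 80%. At 50 per group the break-even ICC is about 0.61 for k = 2 and 0.70 for k = 3.

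**Step 4: power over a range (unadjusted t-test, difference 1.2).**

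| k | ICC | SD(single) | Minimum per group | Power at 41 | Power at 50 |
|---|---|---|---|---|---|
| 2 | 0.9 | 1.95 | 43 | 78.6% | 86.2% |
| 2 | 0.8 | 2.00 | 45 | 76.4% | 84.3% |
| 2 | 0.7 | 2.06 | 48 | 74.0% | 82.2% |
| 2 | 0.6 | 2.12 | 51 | 71.5% | 79.9% |
| 3 | 0.9 | 1.97 | 44 | 77.9% | 85.6% |
| 3 | 0.7 | 2.12 | 51 | 71.5% | 79.9% |

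With two raters, the rise in the minimum over 41 is 2, 4, 7 and 10 per group as the ICC falls from 0.9 to 0.6, against a margin of 9.

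**Step 5: what baseline adjustment could recover.** If baseline tone correlates r with the 10-minute score, the residual SD is SD(single) × √(1 − r²). Setting this to 1.9 with k = 2 gives r = √((1 − ICC)/2): 0.22, 0.32, 0.39 and 0.45 for ICC 0.9, 0.8, 0.7 and 0.6. The documents give no value for r.

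**The case against.** The strongest reply is that nothing has been miscalculated. The protocol's statement is conditional on an SD of 1.9, its source is disclosed, and 41 follows from it. That stands: this is a question about a planning input, not an arithmetic error.

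A reader might go further and infer that 41 per group fails to give 80% power. The documents do not support that. They give neither the number of raters (only that scores were averaged between them) nor the reliability. At ICC 0.9 with two raters the shortfall from 80% is only 1.4 points.

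A reader might also count the time origin, delivery in the earlier study against study drug in the trial, as lost power. It is a genuine mismatch, but its direction is unknown: the SD 10 minutes after the drug could be larger or smaller than 1.9, and a smaller one could offset the rater effect.

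Two further replies have weight:

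- **Fifty per group are randomized.** Over the two-rater range this keeps unadjusted power at about 80% or more. The SAP excludes only 3 patients for missing tone; at 48 per group, power is 78.2% to 84.7% for ICC 0.6 to 0.9. But the protocol gives the margin a different job, and the Protocol Summary withdraws patients whose care departs from the protocol.
- **The SAP adjusts for baseline tone.** A moderate correlation would cancel the larger SD. But both power statements are for a two-sample t-test, no correlation is stated, and the protocol's methods text does not name baseline tone as a covariate. The gain is possible but has not been planned for.

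**Conclusion.** The point holds as a mismatch between the planning SD and the endpoint. The SD of 1.9 is for rater-averaged scores and the endpoint is a single rating, so, other things equal, 1.9 is too small. The stated power has almost no room for this: it falls below 80% once the SD passes 1.916.

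The size rests on assumed values. Under two raters and ICC 0.6 to 0.9, the power stated for 41 per group is too high by roughly 2 to 9 points (80.7% against 78.6% to 71.5%), and the minimum moves from 41 to between 43 and 51. At an ICC of 0.6 the whole margin for protocol violations is taken up; at 0.9, only 2 of the 9 per group. If reliability is close to perfect, or baseline adjustment removes enough variance, there may be no practical loss.

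This justifies correcting a stated figure. It does not show that the trial is too small.

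**What to change.** Recompute the sample size with the single-rater SD from the previous inter-rater study, taken at the time closest to 10 minutes after the second uterotonic. State how many raters were averaged and the ICC. Restate the power at 41 and at 50 per group. If the SAP's baseline-adjusted model is the primary analysis, add the power for that model with the baseline correlation it assumes.

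In the same revision, reconcile the two planning bases: SD 1.9, difference 1.2 and 41 per group in the protocol; SD 1.5, difference 1 and 37 per group in the SAP. The SAP's 37 also reproduces from its own inputs (80.8% power), so the conflict lies in the assumptions. Correcting 1.9 alone would not settle which basis governs.

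The cost is one recalculation, from data the sponsor should hold since the earlier study was about inter-rater reliability, and a slightly less favourable stated figure. The planned 100 randomized need not change.
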